## 2.0 TRIAL DESIGN

### 2.1 Trial design

This is a non-randomized phase II trial in male and female subjects diagnosed with recurrent respiratory papillomatosis (RRP) with extensive laryngeal, tracheal and/or pulmonary involvement. Approximately 22 subjects will be enrolled in this trial to examine the safety and efficacy in this subject population who would be administered up to 200 mg of pembrolizumab every 3 weeks. Subjects will be evaluated every 3 weeks (21 days  $\pm$  3 days) in the clinic with a video-recorded transnasal flexible laryngoscopy and tracheoscopy examination to assess clinical response on treatment (**Appendix A**) as well as evaluated every 24 weeks (169 days  $\pm$  14 days) with CT scans to assess response per volumetric analysis. For those patients with pulmonary lesions measurable by RECIST 1.1, CT scans of the chest will be obtained every 12 weeks (84 days  $\pm$  7 days) to assess response per RECIST 1.1 criteria. In addition, patients will complete quality of life questionnaires to assess preference of pembrolizumab as compared to standard of care treatment, which is surgery, for this patient population (**Appendix F**).

As part of the natural course of this disease, patients undergo operative procedures for repeated debridement of papillomata within their upper aerodigestive tract in order to improve their breathing and/or voice quality. Prior to starting pembrolizumab, subjects will undergo a comprehensive laryngoscopy and tracheobronchoscopy to map and score their disease burden in the upper aerodigestive tract and a pre-treatment biopsy would be obtained at that time. Subsequently, at a minimum of every 12 weeks (84 days  $\pm$  14 days), subjects will be taken to the operating room for a comprehensive laryngoscopy and tracheobronchoscopy and debridement of any papillomatous lesions which obstructs the caliber of their airway by more than 50% and/or other lesions at the discretion of the surgeon. Some patients will require more frequent visits to the operating room depending on their disease burden and associated clinical symptoms. Biopsies will be obtained during all operative visits.

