## **11.2 Adverse Event Definition**

An adverse event is defined as any untoward medical occurrence in a patient or clinical investigation subject administered a pharmaceutical product and which does not necessarily have to have a causal relationship with this treatment. An adverse event can therefore be any unfavorable and unintended sign (including an abnormal laboratory finding, for example), symptom, or disease temporally associated with the use of a medicinal product or protocol-specified procedure, whether or not considered related to the medicinal product or protocol-specified procedure. Any worsening (i.e., any clinically significant adverse change in frequency and/or intensity) of a preexisting condition that is temporally associated with the use of the Merck's product, is also an adverse event.

Changes resulting from normal growth and development that do not vary significantly in frequency or severity from expected levels are not to be considered adverse events. Examples of this may include, but are not limited to, teething, typical crying in infants and children and onset of menses or menopause occurring at a physiologically appropriate time.

Merck product includes any pharmaceutical product, biological product, device, diagnostic agent or protocol-specified procedure, whether investigational (including placebo or active comparator medication) or marketed, manufactured by, licensed by, provided by or distributed by Merck for human use.

Adverse events may occur during the course of the use of Merck product in clinical trials or within the follow-up period specified by the protocol, or prescribed in clinical practice, from overdose (whether accidental or intentional), from abuse and from withdrawal.

Adverse events may also occur in screened subjects during any pre-allocation baseline period as a result of a protocol-specified intervention, including washout or discontinuation of usual therapy, diet, placebo treatment or a procedure.

Progression of the cancer under study is not considered an adverse event unless it is considered to be drug related by the investigator.

---

*CONFIDENTIAL*

*This document is confidential. Do not disclose or use unless authorized.*

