All adverse events will be recorded from the time the consent form is signed through 30 days following cessation of treatment and at each examination on the Adverse Event case report forms/worksheets. The reporting timeframe for adverse events meeting any serious criteria is described in Section 11.0.

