### **11.4 Evaluating Adverse Events**

An investigator who is a treating investigator or qualified designee will evaluate all adverse events according to the NCI Common Terminology for Adverse Events (CTCAE), version 4.0. Any adverse event which changes CTCAE grade over the course of a given episode will have each change of grade recorded on the adverse event case report forms/worksheets.

All adverse events regardless of CTCAE grade must also be evaluated for seriousness.

The causality of SAEs (their relationship to all study treatment/procedures) and the expectedness

---

*CONFIDENTIAL*

*This document is confidential. Do not disclose or use unless authorized.*

will be assessed by the treating investigator(s) and communicated to the Sponsor-Investigator. The causal relationship can be one of the following:

- Related: There is a reasonable causal relationship between study drug administration and the AE.
- Not Related: There is not a reasonable causal relationship between study drug administration and the AE.

---

*CONFIDENTIAL*

*This document is confidential. Do not disclose or use unless authorized.*

Table 6: Evaluating Adverse Events

V4.0 CTCAE Grading	Grade 1	Mild; asymptomatic or mid symptoms; clinical or diagnostic observations only; intervention not indicated.						
	Grade 2	Moderate; minimal, local or noninvasive intervention indicated; limiting age-appropriate instrumental ADL.						
	Grade 3	Severe or medically significant but not immediately life-threatening; hospitalization or prolongation or hospitalization indicated; disabling; limiting self-care ADL.						
	Grade 4	Life threatening consequences; urgent intervention indicated.						
	Grade 5	Death related to AE						

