### 11.5.1 Reporting Requirements

For multi-institution studies where a DF/HCC investigator is serving as the Overall Principal Investigator, each participating institution must abide by the reporting requirements set by the DF/HCC. In addition to SAEs that meet criteria set forth in Section 11.3, the Sponsor requires reporting of any medical event equivalent to an unexpected grade 2 or 3 with a possible, probable or definite attribution, unexpected grade 4 toxicities, and grade 5 (death) regardless of study phase or attribution.

Each investigative site will be responsible to report SAEs that occur at that institution to their respective IRB. It is the responsibility of each participating investigator to report serious adverse events to the study sponsor and/or others as described below.

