The primary efficacy population includes all eligible adult patients who begin protocol treatment. ORR will be summarized as a proportion with corresponding exact 95% confidence interval (CI) (if the trial closes to accrual after the first stage), or a corresponding 95% two-stage CI if the trial closes to accrual after the second stage. Best overall response for the pediatric patients will also be summarized.

Another endpoint is to assess adverse events. Adverse events will be classified and graded according to the CTCAE v.4.0. Frequencies of adverse events will be summarized overall and within adult and pediatric subgroups. Another endpoint is to assess quality of life (QOL). QOL will be assessed via self-report questionnaires at the timepoints outlined in the Study Flow Chart. Descriptive statistics from the questionnaires will be summarized across timepoints of assessment overall and within adult and pediatric subgroups. Rates of drop-out/non-response to QOL assessments and corresponding reason will also be summarized across timepoints of assessment. Secondary objectives include assessment of biomarkers in blood and tissue. Descriptive statistics from the assays will be summarized across timepoints of sample collection overall and within adult and pediatric subgroups. Rates of refusal and/or reason sample not obtained will be summarized across timepoints of assessment.

Various correlative studies will also be performed. Tissue and blood will be collected at baseline and at post-baseline timepoints as outlined in Section 9 and 10.1.2.7. Markers from tissue and blood will be summarized descriptively and graphically overall and within adult and pediatric subgroups. Within subject changes in markers will also be analyzed. Twenty-two adult patients with baseline and a post-baseline values provides 80% power to detect .65 SD mean difference (Wilcoxon sign rank test two-sided 0.05 alpha level). Baseline as well as changes from baseline to a post-baseline timepoint will also be compared between patients whose disease responded (CR,PR) and those whose disease did not respond using the Wilcoxon rank-sum test. Twenty two adult patients provides 82% power (using a two-sided 0.05 alphas level test) to detect a 1.4 SD difference in means assuming that 38% of the patients have disease which responds.

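### Section 11.4 asks for causality to treatment and procedures, but its only two answers, and Table 6, concern the drug, and 14.1 gives adverse events no onset window or attribution split

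*Combined protocol and SAP*

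**What the plan says.** Section 11.2 counts as adverse events those "temporally associated with the use of a medicinal product or protocol-specified procedure", so complications of protocol procedures are included. It also fixes the collection period: "All adverse events will be recorded from the time the consent form is signed through 30 days following cessation of treatment". Section 11.1 starts collection at consent too, and asks for contact beyond 30 days when an event is tied to study procedures or study medication.

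Section 11.4 opens the causality assessment with "The causality of SAEs (their relationship to all study treatment/procedures) and the expectedness". It then allows two answers. 'Related' is "There is a reasonable causal relationship between study drug administration and the AE"; 'Not Related' is "There is not a reasonable causal relationship between study drug administration and the AE". Table 6 asks whether the Merck product caused the event, and its 'No' answer applies when some other cause is obvious.

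Section 11.5.1 requires reporting of "any medical event equivalent to an unexpected grade 2 or 3 with a possible, probable or definite attribution". The table in 11.5.2 groups events as unrelated/unlikely or possible/probable/definite, under the single label of attribution.

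Section 2.1 makes operations part of the protocol: after a baseline endoscopy with biopsy, and at least every 12 weeks, "subjects will be taken to the operating room for a comprehensive laryngoscopy and tracheobronchoscopy and debridement", with biopsies at the operative visits (under 10.1.2.7, only if lesions are present).

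Section 3.1 lists safety and tolerability as the second primary objective. Section 14.1 calls adverse events another endpoint and plans this: "Frequencies of adverse events will be summarized overall and within adult and pediatric subgroups".

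**The concern.** The sentence that introduces the causality judgement and the answers that follow it do not match. The first covers procedures; the answers cannot express them. An investigator who believes a bleed came from the biopsy and not from the drug has only one truthful choice, and that choice also holds every unrelated intercurrent illness.

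This matters more here than in most drug trials. There is one arm, so no control group shows the background rate of surgical complications. Operations recur throughout treatment, and 7.1.2 places the infusion after the operative endoscopy, so drug and surgical events can share a time window. Attribution and onset are then the main means of reading the safety data. The 11.4 scale provides no procedure category, and 14.1 specifies no table by attribution or by onset relative to first dose.

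**Working it through.** The plan states no figure on this point, so there is none to reproduce. The check sets the passages side by side and then gives an illustrative size.

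**1. One event traced through the text.** Take an airway bleed after a protocol operation, judged to be caused by the biopsy and not by pembrolizumab.
- 11.2: it is an adverse event, because it follows a protocol-specified procedure.
- 11.4: 'Related' is false, since it concerns the drug. 'Not Related' is true.
- Table 6: another cause is obvious, so the answer is 'No'.
- 11.1: follow-up beyond 30 days depends on a link to study procedures, but neither 11.4 nor Table 6 has an answer that records the link.
- The broad definition of a Merck product in 11.2 does not help. It reaches only procedures that Merck makes, licenses, provides or distributes.

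**2. Where attribution changes reporting.** In the 11.5.2 table:
- Grade 2-3, expected: not required in either attribution row.
- Grade 2-3, unexpected: not required if unrelated/unlikely; 5 calendar days if possible/probable/definite.
- Grade 4 and Grade 5: the same in both rows.

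SAEs go to the Coordinating Center under 11.5, and under 11.5.3 from consent to 90 days after treatment (or new anti-cancer therapy, if earlier) whether or not they are related. So attribution decides reporting for one group only: non-serious, unexpected Grade 2-3 events. No rule says how the two answers in 11.4 translate into the five terms in 11.5.2, or which cause those terms refer to.

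**3. What 14.1 specifies.** It gives overall, adult and pediatric frequencies. It defines an efficacy population but no safety population, and it gives no onset window and no split by attribution.

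**4. Pre-dose events.** Collection starts at consent, and 11.2 expressly counts events in a baseline period that result from a protocol intervention. However, the baseline endoscopy may be up to 6 weeks before enrollment (flow chart footnote 21), the biopsy up to 42 days before registration (5.1.2), and results from routine care before consent can be accepted (footnote 2). Pre-dose procedure events therefore enter the data only when the baseline procedure follows consent.

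**5. Illustrative size.** Inputs: 24 months of treatment (taken as 104 weeks), an operation every 12 weeks, one baseline operation, and 21 evaluable adults. The per-operation risk p is an assumption; the documents give none. Independence between operations is also assumed.
- On-treatment operations: 104/12 = 8.67, so 8. As a cross-check, every fourth cycle within 35 administrations gives cycles 5, 9, ..., 33, also 8.
- With baseline: 8 + 1 = 9 per completer, and 21 × 9 = 189 if all 21 complete.
- Share of completers with at least one event = 1 − (1 − p)^9. At p = 1%: 1 − 0.99^9 = 8.6%. At p = 5%: 1 − 0.95^9 = 37.0%.
- Expected events if all complete: 189 × 0.01 = 1.9 and 189 × 0.05 = 9.5.
- Without the baseline operation: 1 − 0.99^8 = 7.7% and 1 − 0.95^8 = 33.7%.

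**The case against.** The best case on the other side is that this is a drafting slip with little effect. Much of that case stands.

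- **Reporting.** A reader might infer that 'Not Related' in 11.4 takes unexpected Grade 2-3 procedure events out of expedited reporting. The documents do not establish that. The 11.5.2 scale is separate and not limited to the drug, so a surgical complication could be entered there as definite. SAEs are reported whatever the attribution, 11.5.8 sends all events to the Coordinating Center, and 11.6 puts all of them into routine submissions. What remains is ambiguity in one group of events.
- **Strength of the coding rule.** Table 6 offers its criteria as guidance for clinical judgement, and the case report forms (Appendix G) are not shown, so a procedure field may already exist. The 11.4 definitions would still contradict their own introduction.
- **Analysis.** A reader might infer that 14.1 decides to pool procedure and pre-dose events into the drug's rates. It is silent; it neither includes nor excludes them. Event dates and surgery dates are recorded, so onset can be recovered later. An investigator's judgement of cause cannot be recovered from dates when operation and infusion fall close together.
- **Status of safety.** A reader might call the event frequencies co-primary. Section 3.1 makes safety a primary objective, but 14.1 names only the response rate as primary endpoint, and no test uses the frequencies.
- **Scope of the fix.** Rewording the two answers to cover drug or procedure would remove the contradiction. It would also merge the two causes, which a single-arm safety assessment needs kept apart.

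**Conclusion.** The contradiction in 11.4 is in the text. Causality is said to include procedures, but the permitted answers and Table 6 cannot record it, so on that scale harm from required operations and biopsies is indistinguishable from unrelated illness. Section 11.1 relies on a category that the scale lacks. Whether a non-serious, unexpected Grade 2-3 procedure event is reportable under 11.5.2 is unclear; the documents do not show that it is lost. Section 14.1 leaves onset and attribution unspecified for a primary objective, and pre-dose events may be counted when the baseline procedure follows consent.

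Three limits apply. The phrase on procedures is written for SAEs, although both answers speak of the AE generally. The range of 9% to 37% of completers rests on an assumed 1-5% risk per operation and on completing 24 months. It is also not the extra harm due to the protocol, since repeated surgery belongs to the natural course of this disease and some operations would occur anyway. The response-rate design is unaffected.

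**What to change.** - **11.4 and Table 6:** record two answers per event: related to pembrolizumab (yes/no), and related to a protocol procedure (yes/no).
- **11.5.1 and 11.5.2:** state how these answers map to the attribution terms there, with either yes counting as related.
- **14.1:** tabulate treatment-emergent events, meaning onset or worsening from first dose in all treated patients, for all events, drug-related events and procedure-related events. Keep the adult and pediatric split. List events between consent and first dose separately.

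The cost is one extra field on the adverse event form, if the form lacks it, two table shells, and a few more expedited reports of procedure events. Sample size and the efficacy analysis do not change.

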## 11.5 Expedited Adverse Event Reporting

Investigators must report to the Coordinating Center and Overall PI any serious adverse event (SAE) that occurs after the initial dose of study treatment, during treatment, or within 90 days of the last dose of treatment.

### 11.5.1 Reporting Requirements

For multi-institution studies where a DF/HCC investigator is serving as the Overall Principal Investigator, each participating institution must abide by the reporting requirements set by the DF/HCC. In addition to SAEs that meet criteria set forth in Section 11.3, the Sponsor requires reporting of any medical event equivalent to an unexpected grade 2 or 3 with a possible, probable or definite attribution, unexpected grade 4 toxicities, and grade 5 (death) regardless of study phase or attribution.

Each investigative site will be responsible to report SAEs that occur at that institution to their respective IRB. It is the responsibility of each participating investigator to report serious adverse events to the study sponsor and/or others as described below.

### 11.5.2 Reporting to the Sponsor

Investigative sites within DF/HCC will report AEs directly to the DFCI Office for Human Research Studies (OHRS) per the DFCI IRB reporting policy.

Other investigative sites will report AEs to their respective IRB according to the local IRB's policies and procedures in reporting adverse events. A copy of the submitted institutional AE form should be forwarded to the Coordinating Center within the timeframes detailed in the table below.

Attribution	DF/HCC Reportable AEs				
	Gr. 2 & 3 AE Expected	Gr. 2 & 3 AE Unexpected	Gr. 4 AE Expected	Gr. 4 AE Unexpected	Gr. 5 AE Expected or Unexpected
Unrelated Unlikely	Not required	Not required	5 calendar days #	5 calendar days	24 hours*
Possible Probable Definite	Not required	5 calendar days	5 calendar days #	5 calendar days	24 hours*

# If listed in protocol as expected and not requiring expedited reporting, event does not need to be reported.

\* For participants enrolled and actively participating in the study *or* for AEs occurring within 30 days of the last intervention, the AE should be reported within 1 business day of learning of the event.

Participating investigators must report each serious adverse event to the Coordinating Center in accordance with the table above. In the event that the participating investigator does not become aware of the serious adverse event immediately (e.g., participant sought treatment elsewhere) or within the reporting timeframes listed in the table above, the participating investigator is to

*CONFIDENTIAL*

*This document is confidential. Do not disclose or use unless authorized.*

report the event within 1 business day after learning of it and document the time of his or her first awareness of the adverse event. Report serious adverse events by email or facsimile to:

### **11.5.3 Reporting to Merck**

Any serious adverse event, or follow up to a serious adverse event, including death due to any cause other than progression of the cancer under study that occurs to any subject from the time the consent is signed through 90 days following cessation of treatment, or the initiation of new anti-cancer therapy, whichever is earlier, whether or not related to Merck product, must be reported within 24 hours to the Coordinating Center and within 2 working days to Merck Global Safety.

Non-serious Events of Clinical Interest will be forwarded to Merck Global Safety and will be handled in the same manner as SAEs.

Additionally, any serious adverse event, considered by an investigator who is a qualified physician, to be related to Merck product that is brought to the attention of the investigator at any time outside of the time period specified in the previous paragraph also must be reported immediately to the Coordinating Center and to Merck.

A copy of all 15 Day Reports and Annual Progress Reports is submitted as required by FDA, European Union (EU), Pharmaceutical and Medical Devices agency (PMDA) or other local regulators. Investigators will cross reference this submission according to local regulations to the Merck Investigational Compound Number (IND, CSA, etc.) at the time of submission. Additionally investigators will submit a copy of these reports at the time of submission to FDA.

The Coordinating Center will submit all SAE reports, 15 day reports, FDA reports and any other relevant safety information to Merck & Co., Inc on behalf of the Sponsor at:

### **11.5.4 Events of Clinical Interest**

Selected non-serious and serious adverse events are also known as Events of Clinical Interest (ECI) and must be recorded as such on the Adverse Event case report forms/worksheets and reported within 24 hours to the Coordinating Center and within 2 working days to Merck Global Safety. The Coordinating Center will submit all safety reports to Merck on behalf of the Sponsor.

---

*CONFIDENTIAL*

*This document is confidential. Do not disclose or use unless authorized.*

Events of clinical interest for this trial include:

1. An overdose of Merck product, as defined in Section 11.5.5 - Definition of an Overdose for This Protocol and Reporting of Overdose to the Sponsor, that is not associated with clinical symptoms or abnormal laboratory results.
2. An elevated AST or ALT lab value that is greater than or equal to 3X the upper institutional limit of normal and an elevated total bilirubin lab value that is greater than or equal to 2X the upper institutional limit of normal and, at the same time, an alkaline phosphatase lab value that is less than 2X the upper institutional limit of normal, as determined by way of protocol-specified laboratory testing or unscheduled laboratory testing.\*

*\*NOTE: These criteria are based upon available regulatory guidance documents. The purpose of the criteria is to specify a threshold of abnormal hepatic tests that may require an additional evaluation for an underlying etiology. The trial site guidance for assessment and follow up of these criteria can be found in the Investigator Trial File Binder (or equivalent).*

3. Additional adverse events:

A separate guidance document has been provided entitled “Event of Clinical Interest Guidance Document” (previously entitled, “Event of Clinical Interest and Immune-Related Adverse Event Guidance Document”). This document can be found in Appendix 4 and provides guidance regarding identification, evaluation and management of ECIs and irAEs.

ECIs (both non-serious and serious adverse events) identified in this guidance document from the date of first dose through 90 days following cessation of treatment, or 30 days after the initiation of a new anticancer therapy, whichever is earlier, need to be reported within 24 hours to the Coordinating Center and within 2 working days to Merck Global Safety regardless of attribution to study treatment, consistent with standard SAE reporting guidelines.

Subjects should be assessed for possible ECIs prior to each dose. Lab results should be evaluated and subjects should be asked for signs and symptoms suggestive of an immune-related event. Subjects who develop an ECI thought to be immune-related should have additional testing to rule out other etiologic causes. If lab results or symptoms indicate a possible immune-related ECI, then additional testing should be performed to rule out other etiologic causes. If no other cause is found, then it is assumed to be immune-related.

